8.1 Statistical and Analytical Plans

A statistical analysis plan (SAP) will be prepared and finalized prior to database lock. The SAP will ensure that the study data listings, summary tables, and figures that will be produced, and the statistical methodologies that will be used, are complete and appropriate to allow valid conclusions regarding the study objectives.

8.1.1 Datasets or Populations Analyzed

The Safety Set (SS) will include all subjects who applied at least 1 Viaskin patch. Subjects will be analyzed according to treatment received. In case of wrong dispensation, the subject will be analyzed according to the treatment received the longest, or as it will be determined at the Blind Data Review Meeting (BDRM), on a case-by-case basis. The SS will be used for all safety analysis tables and listings.

The Intent-to-Treat Set (ITT) will include all randomized subjects. Subjects will be analyzed according to randomized treatment. The ITT Set will be used for all analyses of efficacy endpoints.

The Per Protocol Set (PPS) will include all subjects from the ITT population who do not have major protocol violations that may affect the primary endpoint. Major protocol deviations will be defined in the SAP.

Protocol deviations will be categorized as either major or minor and discussed during the blinded data review meeting (BDRM). Decisions taken at the BDRM will be documented and approved by DBV prior to database lock and unblinding the study.

The Open-label Sets (OLS) will include all subjects from the ITT who entered the open-label treatment period (ie, who applied at least one Viaskin Milk patch during the open-label treatment period) and will be described in the SAP.

The Open-label Set 300 µg (OLS_300) will include all subjects who switched to Viaskin Milk 300 µg and will be described in the SAP.

8.1.2 General Considerations

There will be 2 age groups considered for the statistical analyses:

- Children: 2 to 11 years of age at the time of Visit 1
- Adolescents: 12 to 17 years of age at the time of Visit 1

Data will be summarized by age group, dose level, and pooled placebo group for the randomized blinded treatment period (Months 0 to 12) as follows:

Part A and Part B: Viaskin Milk 150 µg, 300 µg, 500 µg of cow's milk proteins, and placebo.

Part A and Part B subjects will be combined and pooled by dose level, as applicable, for the efficacy analyses at Month 12.

In general, categorical data will be summarized using counts and percentages, and continuous variables will be summarized using the number of subjects with evaluable

data (n), mean, standard deviation, median, first and third quartiles (Q1, Q3), minimum and maximum.

All hypothesis tests will be in scope of dose-response or longitudinal analyses.

Listings of raw subject data will be sorted by dose level, randomization number and visit, as applicable, for all randomized subjects. For subjects in Part A, data from Cohorts 1, 2, and 3 will be presented separately in the listings.

8.1.3 Subject Disposition

The number and percentage of subjects in each analysis population (ITT, PPS, SS, OLS and OLS_300) will be summarized overall and by treatment group (dose level/placebo).

Subject disposition will be summarized for all subjects in the ITT. The number and percentage of subject completed, discontinued, and the primary reason for early withdrawal from the study will be tabulated by dose level and placebo group.

8.1.4 Demographic and Other Baseline Characteristics

For continuous demographic variables and baseline characteristics (including age, height, weight, body mass index (BMI, kg/m²), body surface (m²), weight/height (kg/m), SPT mean wheal diameter, FEV₁ percent predicted [spirometry], PEF percent predicted, CRD of cow's milk, and milk sIgE), descriptive will be generated for each dose level and placebo group at Visit 1 for all subjects in the ITT.

For categorical demographic variables and baseline characteristics (including sex, ethnic origin, and medical history), the number and percent of subjects in each category will be tabulated for each dose level and placebo group at Visit 1 for all subjects in the ITT.

The same descriptive summaries will be repeated at the entry of the Open-Label period and at the entry of the switch to Viaskin Milk 300 µg.

Individual subject demographic and baseline characteristics data will be listed.

8.1.5 Concomitant Medications

Concomitant medications will be coded using the World Health Organization Drug Dictionary (WHODrug). A summary of concomitant medications by the second level Anatomical Therapeutic Chemical (ATC) term and preferred term will be produced overall and by age group, for each dose level and placebo group on the ITT for the randomized blinded treatment period (Months 0 to 12).

Concomitant medications during the open-label treatment periods after Month 12 will be described. Details will be provided in the SAP.

8.1.6 Efficacy

Missing data will not be imputed for the efficacy analyses except for the classification of treatment responders / non responders for the primary efficacy analysis.

8.1.6.1 Primary Efficacy Endpoint and Analysis

The primary efficacy endpoint will be the percentage (%) of subjects who are treatment responders after 12 months of EPIT treatment.

A treatment responder is defined as a subject who meets at least one of the following criteria:

- A \geq 10-fold increase in the CRD of cow's milk proteins at the Month 12 DBPCFC as compared to baseline value and reaching at least 144 mg of cow's milk proteins (approximately 4.5 mL of milk).
- A CRD of cow's milk proteins \geq 1444 mg (approximately 45 mL of milk) at the Month 12 DBPCFC.

The CRD of cow's milk proteins is entered directly in CRF by the sites and is calculated as the sum of all doses of cow's milk proteins given during the challenge, including repeat doses if applicable, and exact quantity of the last dose given (if not given in totality).

The percentage of subjects who are treatment responders after 12 months of EPIT treatment will be calculated on the ITT population using missing = failure imputation method (ie, subjects with missing observation at Month 12 will be considered as non-responders).

The number and percentage of responders will be summarized overall and by age group, for each pooled dose level (Part A and Part B) and placebo group, for the blinded treatment period (Months 0 to 12).

Methods of exact logistic regression will be used to compare the proportion of treatment responders at Month 12 in each dose level to placebo, adjusting for age group, and including the treatment group as fixed effect, for subjects in the ITT population. P-values, odds ratios together with associated 95% Confidence Intervals (95% CI) will be presented.

The primary efficacy endpoint of this study, together with additional exploratory analyses, will assess the dose-response relationship and aim to inform the dose selection for phase 3. Model-based analytical approaches of exploratory dose finding (e.g., MCP-Mod) will be used to evaluate the dose-response relationship and estimate target dose(s).

Further details of the statistical methodology and considerations for the approaches to be used in the analysis will be specified in the SAP.

8.1.6.1.1 Sensitivity analyses on Primary efficacy criteria

Sensitivity analyses will be performed in order to evaluate the impact of the primary efficacy criteria to the results and interpretation of study results. The analysis described above will be repeated for subjects in the ITT using observed data and in the PPS. A similar analysis will be performed on ITT population using multiple imputation instead of missing = failure imputation method. Multiple imputation method will be further described in the SAP.

Other covariates of interest including baseline IgE (by levels) and country will be explored.

Finally, the primary efficacy analysis will be repeated for each age group as well as for each filaggrin mutation group (With filaggrin mutation / Without filaggrin mutation). Within subgroup, the treatment group comparisons will be conducted at a two-sided 10% significance level.

8.1.6.2 Secondary Efficacy Endpoints and Analysis

The secondary endpoints for the double-blind, placebo-controlled treatment period up to Month 12 are:

- The mean and median CRD of cow's milk proteins at Month 12 and change from baseline.
- The change from baseline value in levels of sIgE and allergen-specific immunoglobulin G4 (sIgG4) to cow's milk at all timepoints evaluated up to Month 12.
- The change from baseline value in levels of sIgE and sIgG4 to caseins, α -lactalbumin, and β -lactoglobulin at all timepoints evaluated up to Month 12.
- The change from baseline in SPT wheal at all timepoints evaluated up to Month 12.
- The change in the severity of symptoms elicited during the milk DBPCFC from baseline to Month 12.
- The change from baseline in Quality of Life (QoL) assessments at Month 12.

The endpoints after Month 12 for the open-label treatment periods with Viaskin Milk 500 μ g up to 48 months and Viaskin Milk 300 μ g for 24 months are:

- The percentage of subjects who are treatment responders over the course of open-label treatment with Viaskin Milk 500 μ g and 300 μ g.
- The CRD of cow's milk proteins over the course of open-label treatment with Viaskin Milk 500 μ g and 300 μ g.
- The levels of sIgE to cow's milk over the course of open-label treatment with Viaskin Milk 500 μ g and 300 μ g.
- The levels of sIgG4 to cow's milk proteins over the course of open-label treatment with Viaskin Milk 500 μ g.
- The levels of sIgE and sIgG4 to caseins, α -lactalbumin, and β -lactoglobulin over the course of open-label treatment with Viaskin Milk 500 μ g and 300 μ g.
- The SPT wheal over the course of open-label treatment with Viaskin Milk 500 μ g and 300 μ g.
- The severity of symptoms elicited during the milk DBPCFC over the course of open-label treatment with Viaskin Milk 500 μ g and 300 μ g
- The QoL assessments over the course of open-label treatment with Viaskin Milk 500 μ g and 300 μ g.

8.1.6.2.1 Treatment Responders

Treatment responders during the open-label treatment periods after Month 12 will be explored. Details will be provided in the SAP.

8.1.6.2.2 Cumulative Reactive Dose (CRD) of Cow's Milk Proteins

The CRD and changes from baseline will be summarized overall and by age group, dose level group (Part A and Part B pooled), and timepoint on the ITT for the randomized blinded treatment period (Months 0-12).

CRD during the open-label treatment periods after Month 12 will be explored. Details will be provided in the SAP.

8.1.6.2.3 Immunological Markers

All analyses will be carried out on the ITT population.

Absolute values and changes from baseline for the immunological markers were to be summarized overall and by age group, dose level and placebo groups, and timepoint for the randomized blinded treatment period (Months 0 to 12).

Longitudinal analyses will be explored for each of the following parameters:

- cow's milk sIgE and sIgG4 (cow's milk sIgG4 will not be collected after the switch to Viaskin Milk 300 µg)
- sIgE and sIgG4 to
 - caseins,
 - α -lactalbumin, and
 - β -lactoglobulin.

Details will be provided in the SAP.

Immunological markers during the open-label treatment periods after Month 12 will be explored. Details will be provided in the SAP.

8.1.6.2.4 Skin Prick Test

SPT at all timepoints evaluated will be summarized using descriptive statistics overall and by age group, dose level and placebo group on the ITT for the randomized blinded treatment period (Months 0 to 12).

The change from baseline (Visit 1) will be assessed using the ratio of the average wheal diameter at each time point *versus* baseline, derived as improvement (if the ratio of the average wheal diameter ≤ 0.75) / no significant improvement (if the ratio of the average wheal diameter > 0.75) and will be compared between each dose level group and placebo, at each respective visit up to Month 12 using the chi-square test or exact logistic regression (same model as for the primary criteria) in case of low sample sizes (at least one theoretical frequency lower than 5).

The number of subjects with a mean wheal diameter equals to 0 will be presented.

Longitudinal analyses will be explored for SPT average wheal diameter. Details will be provided in the SAP.

SPT during the open-label treatment periods after Month 12 will be explored. Details will be provided in the SAP.

8.1.6.2.5 Analysis of Severity During the Milk DBPCFC

The change in the severity of symptoms elicited during the milk DBPCFC from baseline will be assessed at Month 12. Grading of symptoms will be done using the grading definition in the OFC Symptom Score Sheets. Each symptom (objective and subjective) will be graded 0, 1, 2 or 3. A total symptom score will be derived for objective symptoms. The total summary score (absolute and change from baseline) will be summarized overall and by age group, dose level and placebo group on the ITT for the randomized blinded treatment period (Months 0 to 12).

A second severity score will be derived to assess the change from Baseline in the severity of symptoms elicited during the milk DBPCFC at comparable cow's milk proteins dose. The calculation of this severity score at comparable cow's milk proteins dose will be further described in the SAP. This score will be summarized overall and by age group, dose level and placebo group, and timepoint on the ITT for the randomized blinded treatment period (Months 0 to 12).

Longitudinal analyses will be explored for severity score. Details will be provided in the SAP.

Time-to-first objective symptom at Month 12 will be summarized and Kaplan-Meier curves will be provided. Patients without any objective symptom during the DBPCFC will be censored at the time of discharge.

Analysis of severity of symptoms during the open-label treatment periods after Month 12 will be explored. Details will be provided in the SAP.

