symptom appear(s), that would be the end of the food challenge. If only (a) subjective symptom(s) still persist(s) with no appearance of an objective symptom, the next highest dose is then given to the subject, and the challenge should continue until the appearance of a clear objective symptom, at which time the challenge will be stopped.

Complete information of all reactions (objective and subjective symptoms) that occurred during the DBPCFC will be reported in the eCRF, along with information about the doses of cow's milk proteins or placebo administered, time of dose administration, first time of appearance of each symptom, severity grades of each symptom, time of appearance of each severity grade, and medication(s)/treatment(s) given to the subject to treat these symptoms.

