8.2.5 Analysis of Severity during the Milk DBPCFC

8.2.5.1 Double-blind Month 12 and OL-500 analyses

The number of subjects with any objective and subjective allergic reaction during the different DBPCFC for both formulas was summarized overall and for each age group, in total and by (initial randomized) treatment group (placebo/dose level/overall active) for ITT, and OLS-500, respectively.

For the milk formulas only, the number of subjects with the specific objective and subjective allergic reaction during the different DBPCFC were summarized overall and for each age group, in total and by (initial randomized) treatment group (placebo/dose level/overall active) for ITT, and OLS-500, respectively.

The severity of symptoms elicited during the milk DBPCFC were assessed at Screening, Months 12, 24, 36 and 48. Grading of symptoms were done using the grading definition in the Oral Food Challenge (OFC) Symptom Score Sheets. Each symptom (objective and subjective) will be graded once per DBPCFC-Visit.

A total objective severity score was derived as the sum of the severity grades (0, 1, 2 or 3) of the following objective symptoms: pruritus, urticaria/angioedema, rash, sneezing/itching, nasal congestion, rhinorrhea, laryngeal, wheezing, diarrhea, vomiting, cardiovascular and conjunctivitis for DBPCFC with cow's milk formula.

A total subjective severity score was derived as the sum of the severity grades (0, 1, 2 or 3) of the following subjective symptoms: itchy mouth, itchy throat, nausea and abdominal pain for DBPCFC with cow's milk formula.

The total objective and subjective severity score was summarized (absolute and change from baseline) overall and for each age group, in total and by (initial randomized) treatment group (placebo/dose level/overall active), at Screening and Month 12 for subjects on the ITT in the randomized blinded treatment period.

Time-to-first objective symptom at Months 12, was summarized and Kaplan-Meier curves were provided for Month 12, overall and for each age group, in total and by randomized treatment-group (dose level/placebo/overall active). Patients without any objective symptom during the DBPCFC were censored at the time of discharge.

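### The SAP omits the protocol's Month 12 severity score at comparable milk dose without saying so, and the totals it keeps are not matched on dose

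*Protocol*

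**What the plan says.** Change in severity of challenge symptoms from baseline to Month 12 is a named secondary endpoint (Protocol 8.1.6.2, SAP 4.2.1). Protocol 8.1.6.2.5 plans two measures for it. The first is a total score over objective symptoms. For the other, "A second severity score will be derived to assess the change from Baseline in the severity of symptoms elicited during the milk DBPCFC", at a comparable milk protein dose. The protocol adds: "The calculation of this severity score at comparable cow's milk proteins dose will be further described in the SAP". It also fixes the reporting: "This score will be summarized overall and by age group, dose level and placebo group, and timepoint on the ITT", for the blinded period. These are firm commitments; the same section says only that longitudinal analyses of the severity score will be explored.

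SAP 8.2.5.1 contains the following:

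- counts of subjects with reactions;
- an objective total: "A total objective severity score was derived as the sum of the severity grades (0, 1, 2 or 3) of the following objective symptoms";
- a subjective total: "A total subjective severity score was derived as the sum of the severity grades (0, 1, 2 or 3) of the following subjective symptoms";
- time to first objective symptom at Month 12.

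On the unit of grading it says: "Each symptom (objective and subjective) will be graded once per DBPCFC-Visit". SAP 8.2.5.2 (OL-300) takes the worst intensity per symptom and visit. Neither section mentions a comparable dose, and no redaction is marked in SAP 8.2.5.

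SAP section 12 is the log of departures from the protocol. It does not list this omission under any amendment, and it reports no change for Amendments 5 and 6, although the current protocol still contains the score.

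**The concern.** An analysis promised for a named secondary endpoint has dropped out between protocol and SAP with no reason given. Anyone who follows the SAP will not produce it, and anyone who checks section 12 will not learn that it is missing.

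The loss has substance because the omitted score is the only planned measure of severity that holds dose constant. A Month 12 challenge goes on past the screening ceiling when no objective reaction stops it. A subject whose reactive dose has risen is therefore graded after more milk than at baseline, while a subject whose reactive dose has not moved is graded at the same dose. The change in total score then mixes two things: how severe the symptoms are, and how much milk was taken to produce them. That mixture varies with response to treatment, so it differs between arms if the product works.

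**Working it through.** **1. Dose ladders** (Protocol 7.3.1.1.1 and 7.3.1.1.2)

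- Screening: 1, 3, 10, 30, 100, 300 mg. Running sums: 1, 4, 14, 44, 144, 444 mg.
- Month 12: the same, then 1000, 2000, 3000 mg. Further sums: 444 + 1000 = 1444; 1444 + 2000 = 3444; 3444 + 3000 = 6444 mg.

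**2. The plan's own figures.** The responder thresholds in Protocol 8.1.6.1 and SAP 4.1 are reproduced exactly: 1 + 3 + 10 + 30 + 100 = 144 mg, and 144 + 300 + 1000 = 1444 mg.

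**3. Ratio of the ceilings.** 6444 / 444 = 14.5. This compares the ends of the two ladders. It is not a typical subject's dose gap, and it is not a shift in score.

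**4. Smallest dose gap in a responder.** A responder has either a Month 12 CRD of at least 10 times baseline and at least 144 mg, or a Month 12 CRD of at least 1444 mg. For each baseline CRD, take the lowest ladder sum that qualifies and divide by baseline:

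| Baseline CRD (mg) | Lowest qualifying Month 12 CRD (mg) | Ratio |
|---|---|---|
| 1 | 144 | 144 |
| 4 | 144 | 36 |
| 14 | 144 | 10.3 |
| 44 | 444 | 10.1 |
| 144 | 1444 | 10.0 |
| 444 | 1444 | 3.25 |

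So every responder on the standard ladder is scored at 3.25 times the baseline cumulative dose or more, and at 10 times or more unless baseline was 444 mg. Repeated or partial doses move these figures. With the 300 mg dose repeated at screening, for example, baseline is 444 + 300 = 744 mg and the ratio is at least 1444 / 744 = 1.9.

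**5. Data for a matched score.** Protocol 7.3.1.1.3 requires the eCRF to hold doses, dose times and the "severity grades of each symptom, time of appearance of each severity grade". If that was done, grades can be assigned to doses. The SAP's statement of one grade per symptom per challenge visit casts doubt on whether it was done in the blinded period.

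**6. What cannot be computed.** The documents give no distribution of severity scores, so neither the size nor the direction of the effect on the total score can be derived.

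**The case against.** The strongest reply is that the consequence is limited. The endpoint as worded does not mention dose matching. The protocol's first measure, the objective total, is kept. CRD is analysed by ANCOVA and by a non-parametric method (SAP 8.2.2.1), and time to first objective symptom is kept as well. The severity scores are only summarised descriptively, and neither the primary comparison nor dose selection uses them. All of this is correct, and it limits the importance of the point. It does not fill the gap, because CRD and time to onset do not measure severity at a matched dose.

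A reader might go further and infer that the total score is biased against effective doses, since responders react at higher doses and so might show higher grades. The documents do not support that. Screening and Month 12 challenges stop under the same symptom rules, which holds both totals near a common threshold. A subject with no objective symptom through 3000 mg has an objective score of 0 and looks better. Responders could look worse, but nothing in the documents shows that they would.

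A matched score also has a weakness of its own. If the reactive dose rises, Month 12 is cut off at a dose the subject passed without meeting a stopping rule, while baseline keeps its stopping-level grades, so some improvement is nearly built in. If the reactive dose falls, the reverse holds. The score therefore partly restates CRD change. That has to be said when it is reported, but it does not justify dropping a promised analysis in silence.

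Finally, the Month 12 data have been unblinded and reported (SAP 11.1). A definition written now is post hoc.

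**Conclusion.** The point stands as an undisclosed omission of a promised secondary analysis. The totals that remain compare reactions at different doses whenever the reactive dose changes: by at least 3.25-fold for any responder on the standard ladder, and at least 10-fold unless baseline CRD was 444 mg. They cannot be read as change in severity at a given dose. The direction of any distortion is unknown, and the primary result is not affected.

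This assumes standard ladders without repeated or partial doses, and that SAP 8.2.5 is complete as published. SAP section 2 says that double-blind analyses scheduled in versions 4.0 to 6.0 and run are kept in the document, which suggests that this score was not among them. The documents do not show what the 12-month report contains.

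A reader might also expect the score in OL-300. The protocol commits to it for Months 0 to 12 only. The OL-300 challenges use different stopping rules (Protocol 7.3.1.1.3), so matching on dose alone would not make them comparable with screening.

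**What to change.** 1. Confirm that grade times were captured at screening and Month 12, and reconcile Protocol 7.3.1.1.3 with the one-grade-per-visit statement in SAP 8.2.5.1.
2. If they were, add a definition to SAP 8.2.5.1. For example: for each subject, find the lower of the two last doses given (screening and Month 12); for each objective symptom take the highest grade reached by that dose, counting only grades whose recorded time falls before any higher dose was given; sum over symptoms. Summarise the change by arm on the ITT. For a subject stopped at 30 mg at screening and at 300 mg at Month 12, only Month 12 grades timed before the 100 mg dose would count.
3. Label the analysis post hoc, and note that the score partly reflects CRD change.
4. If grade times are missing, or the score is not produced, list its removal with the reason in SAP section 12 and state beside the total scores that they are not dose-adjusted.

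The cost is one SAP paragraph and one derived variable with its summary table, with no new data if the grade times exist. The alternative in step 4 costs a sentence or two.
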